We confirm that no clinical interventions will be made at a participant level during this PoC study as a result of any data collected. Our research is purely observational and will be based on historic rather than real-time data analysis. We can also confirm that all our participant data will be pseudonymised, deidentified and stored securely.

The device readings are blinded to the participants in order to avoid any feedback of the reading that may influence behaviour and ensure that the study remains non-interventional in their usual care. We will also use software based sensors that use the camera on a smart phone or iPad, and web based questionnaires to collect a richer data pool. We will additionally ingest confidential and pseudonymised Health and Social Care and Environmental data and store it all together in a cloud-based platform purpose-built for healthcare, utilising leading technologies and practices in security and privacy. Data scientists and researchers will perform data analysis and model development within the cloud-based platform using the Philips "Workbench" platform. This provides a collaborative development environment with tools that manage the end-to-end process of analytics, analytics asset creation, deployment and support.

8

IRAS ID: 286225 CPMS: 44344 01/08/2020 [Proof of Concept – Smart Technology – South Lincolnshire] PoC Protocol Version: 1.4 Suitable potential participants will be identified by their GP based on set inclusion and exclusion criteria provided by the research team. Participants will either be living in their own residence, in a residential or nursing care home. Informed consent will then be sought according to the recruitment process described in section 3 of this document.

To find the suitable participants the research team will apply **Diagnostic Stratification Technique** algorithms based on Machine Learning, Neural Networks and Artificial Intelligence (AI) to analyse clinical patterns from de-identified patients. These patients' details will already be stored in the NHS in databases such as Hospital Episode Statistics (HES) which is a data warehouse containing details of:

- All admissions
- Outpatient activity
- A & E attendances
- GP data
- Social Care records

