2.1 Testing the hypothesis

The principal research question is to test the hypothesis:

"If information about patient behaviour, conditions and events, captured from wearables and other smart technologies can predict demand for services, then providing these technologies to patients and using the data generated, will enable providers to pre-empt and redirect demand or design new services."

9

The hypothesis will be tested by deploying smart technologies with sensor-based wearables, software sensors using the camera on a smart phone or tablet, and web based questionnaires to study data from the participants.

We will further include pseudonymised Health and Social Care and Environmental data and store it together in a cloud-based platform purpose-built for healthcare, utilising leading technologies and practices in security and privacy.

Data scientists and researchers will perform data analysis and model development within the collaborative development environment with tools that manage the end-to-end process of analytics, analytics asset creation, deployment and support.

We will also be testing whether the use of multiple smart technologies of this nature, is acceptable to patients, easy to use and comfortable.

The analytics will seek to understand whether the use of such technologies and the data gathered from them, can indeed provide useful information in predicting adverse healthcare events and therefore inform the transformation of health services to make interventions sooner to achieve better outcomes.

3. Study design

A high-level outline of the research study design is illustrated below in Table A.

Table A: High Level Outline of Research Design

Our research is observational only and based on historic data. No clinical interventions to a patient's usual care will be made during the study as a result of any data collected. All the data collected will be pseudonymised and will not be monitored or analysed in real time.

The participant will not be able to see the physiological health readings recorded by the smart technologies and so will not have new information about their health which might prompt them to contact their GP or other healthcare services. Therefore, the clinical care of the patient will continue as normal by their GP and/or other health care professionals. This will be fully explained to participants during the recruitment and consenting process.

10

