3.4 Participant onboarding

3.4.1 Allocation of devices

Once participants have provided their consent, each will receive a phone call from Optima Systems Ltd to:

- Ensure the information provided is correct
- Check that the participant is still happy to proceed
- Reiterate the key points of information provided in the Participant Information Sheet
- Establish the current technical capability of each participant i.e. WiFi connectivity

We intend to choose the most suitable smart technology for each patient. The choice of the smart technology is based on careful judgement and we will aim to develop an approximate "right app or wearable for the right patient" as clearly as we can. We will do this based on the initial conversation held with the participant.

Since patients do not necessarily become ill with the same conditions they already have, one or at most two devices per patient will be chosen. We are aiming to include about a third of the patients from residential and care homes since they will tend to be more vulnerable and more likely to have an adverse health event and certain apps can be used by smart devices can be installed from the internet.

The questionnaires will be sent and completed by the patient on the smart phone, tablet or desktop. We currently are considering how we can safely use the same tablet in a Care home to obtain clinical information on respiratory and heart rate and BP oxygen saturation on several patients. This will involve engaging with the residential and care home staff to develop safe procedures; this will be helped by the knowledge of the Covid-19 status of both patients and staff in terms of blood antibody tests on all the staff and all the patients. We hope also that the availability of PPE (Personal Protective Equipment) will be confirmed in each of the relevant homes.

The next action will be to arrange for the participants to receive the wearable or smart technology and to be shown how to use it by the "research supporter" with the aid of the internet. We will be allocating participants randomly according to their circumstances, to receive two (or at most three) wearables or smart technologies.

Commented [CP3]: Updated slightly as we have concluded device allocation will be random to an extent – please ensure my wording is accurate here

Commented [**CP4**]: I think we should go further here and propose a process otherwise it is quite a big question mark this will link back to the SOP you are developing [name].

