Commented [**CP5**]: Can we say – "Optima will then post devices and instructions on how to use them to participants. As soon as the participant receives their devices they will be able to start using them to take health measurements straight away. If a participant has any difficulty in using their devices, they will be able to call Optima Systems for support and guidance".

IRAS ID: 286225 CPMS: 44344 01/08/2020 [Proof of Concept – Smart Technology – South Lincolnshire] PoC Protocol Version: 1.4 15

Device / App name	Physiological measurement	Characteristics of	device / app	Participants
LifeLight	 Respiratory & heart rate, BP & pO₂ 	Digital camera on iPad		As many as possible – proportion shared in Care homes – readings daily
Thermometer	Temperature	Hand held the	rmometer	All participants for 6 days/week
FibriCheck	• ECG – (FIBRICHECK)	Visual Plethysn	nography	300 participants – daily readings
Device / App name	Behavioural	measurements		
GENEactive	 Activity inter 	Activity intensity / duration &		500 participants
Band	frequency/ sleep quality			Daily readings
QuestLink	 Mental, social and physical health status and progression. Measures of patient self-confidence (HCS) and Health Status (howRU) 		All participan	ts - on average twice weekly

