QuestLink enables surveys to be automatically scheduled and distributed to the participants devices. This will include measures of participants self-confidence (Health Confidence Score) and Health Status (howRU) for participants with multimorbidity; mental health, social and physical health status, and progression; current medication and changes and others. It will also include the use of a handheld thermometer to enter the temperature 6 times a week.

TABLE B – Measurement details, devices and details of device/app

Physiological measurement	Device / App name	Characteristics of device / app
Respiratory rate	LifeLight	Digital camera on iPad
Oxygen saturation	LifeLight	Digital camera on iPad
Blood pressure	LifeLight	Digital camera on iPad
Temperature	Thermometer	Hand held thermometer
• ECG – (FIBRICHECK)	FibriCheck	Visual Plethysmography

Behavioural measurements	Device / App name	Characteristics of device / app
Activity intensity / duration & frequency	ActivInsights Band	Wearable Band
 Sleep / Circadian cycle / Sleep time and duration & quality 	ActivInsights Band	Wearable Band
Acceleration monitor for bone health	ActivInsights Band	Wearable Band

18

IRAS ID: 286225 CPMS: 44344 01/08/2020 [Proof of Concept – Smart Technology – South Lincolnshire]

PoC Protocol Version: 1.4

Rehabilitation balance and safety in falls patients	ActivInsights Band	Wearable Band
• Mental, social and physical health status and progression. Measures of patient self-confidence (HCS) and Health Status (howRU)	QuestLink	Cloud based Response to questions – personalised and automatically scheduled and distributed to participant devices

Environmental & Social determinants of health		
Air quality - pollutants	Sensor Related to postal code	Static – accessed from "public sites"
Postcode or GP Postcode –	First digits of postcode	Static data
Lincolnshire Research Observatory (LRO)	Index of Multiple Static – accessed from "public sites Deprivation (IMD)	

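### The protocol says device readings are hidden from participants, but temperature is read and typed in by hand, so it cannot be treated as a blinded predictor of service contacts

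*Protocol*

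**What the plan says.** Two places in the protocol describe blinding of readings. Section 1.3 is general: "The device readings are blinded to the participants in order to avoid any feedback of the reading that may influence behaviour". Section 3 (Study design) says: "The participant will not be able to see the physiological health readings recorded by the smart technologies". It then draws the consequence that participants "will not have new information about their health which might prompt them to contact their GP or other healthcare services".

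Three other places describe how temperature is collected. The device table in section 3.4.1 lists the thermometer in the column for devices and apps, with temperature as its physiological measurement, and assigns it to "All participants for 6 days/week". The QuestLink entry in section 4.1 describes the "use of a handheld thermometer to enter the temperature 6 times a week". The text of section 3.4.1 says who fills in QuestLink: "The questionnaires will be sent and completed by the patient on the smart phone, tablet or desktop".

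The hypothesis in section 2.1 is that data "captured from wearables and other smart technologies can predict demand for services". Section 4.2 lists GP and other healthcare-professional attendances during the study among the linked NHS data.

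**The concern.** The protocol gives a sound reason for hiding readings: a reading that is seen may change behaviour, and behaviour includes contacting services. It then collects one vital sign, from everyone, in a way that appears to require the value to be seen.

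What is at stake is how temperature's predictive performance is interpreted. If a participant or carer sees a raised value and calls the GP because of it, the model records a high temperature followed by a contact. Part of that association exists because the number was shown. It would not carry over to a system in which the signal is collected passively and kept from the patient, which is how the protocol describes its readings. Infections, with Covid-19 among them, are listed events in Table C (section 4.3), so temperature is a plausible signal for this to happen with.

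**Working it through.** The protocol derives no figure for this point, so the main check sets the statements side by side.

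1. **Scope of the blinding.** Section 1.3 covers device readings without exception. Section 3 covers physiological readings from the smart technologies and infers that no new health information reaches the participant.
2. **Is the thermometer within scope?** The table in section 3.4.1 and Table B in section 4.1 both list it as a device or app, with temperature as a physiological measurement. The section 1.3 statement therefore covers it. The inference in section 3 fails whether or not a thermometer counts as a smart technology, because a temperature that has been seen is new health information.
3. **Who sees the value?** It comes from a handheld thermometer and is entered into a questionnaire that the patient completes. Entering a value requires reading it. The protocol does not say so in those words; it follows from the method of capture. In care homes, expected to supply about a third of participants or fewer (section 3.2.2), the protocol does not say who takes or enters the temperature. If staff do, staff see it.
4. **Is there an exemption?** None was found in the protocol.
5. **Does it reach the outcome?** Yes, for contacts that a patient or carer can initiate, since GP and other attendances in the study period are linked.

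**Number of visible readings.** Inputs: 6 readings a week (sections 3.4.1 and 4.1), about six months taken as 26 weeks (section 1.3), and 500 participants (section 3.1). Per participant: 6 × 26 = 156. In total: 156 × 500 = 78,000. This assumes full recruitment and full adherence.

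**Direction of the bias, on assumed inputs only.** Suppose temperature has no true predictive value. Let b be the probability of a contact in a week, and q the probability that a seen raised reading prompts a contact that would not otherwise have occurred. The apparent risk ratio for contact after a raised reading is then [b + q(1 − b)] / b. For b = 5% and q = 5%: (0.05 + 0.05 × 0.95) / 0.05 = 0.0975 / 0.05 = 1.95.

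| b per week | q = 0 | q = 5% | q = 10% | q = 30% |
|---|---|---|---|---|
| 2% | 1.0 | 3.45 | 5.9 | 15.7 |
| 5% | 1.0 | 1.95 | 2.9 | 6.7 |
| 10% | 1.0 | 1.45 | 1.9 | 3.7 |

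With the reading hidden (q = 0) the ratio is 1. With it seen, a useless predictor looks useful. Neither b nor q appears in the protocol, so the table shows direction and sensitivity and is not an estimate for this study.

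**The case against.** **A plain thermometer is not a smart technology.** Section 3 limits its sentence to smart technologies, which section 2.1 describes as wearables, camera software and web questionnaires. This is a fair reading of that one sentence. It does not rescue the general statement in section 1.3, nor the conclusion in section 3 that no new health information arises.

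**Participants would be told something untrue.** A reader might infer this, because section 3 promises a full explanation at consent. The documents do not show it. The information sheet is not available, and the consent items in section 3.3.2 contain no blinding statement and have participants agree to take their own readings. The promise in section 3 follows directly on the sentence about usual care continuing, so what it covers is ambiguous. What stands is a risk that participant material repeats the unqualified claim.

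**Every participant is unblinded.** This is also tempting and also not established. All are assigned a thermometer, but in care homes the person who sees the value may be a member of staff. The route to a contact would then be staff action, not self-referral.

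**The study is no longer non-interventional.** The protocol rests that description on several grounds: no clinical intervention resulting from the data, historic analysis and no real-time monitoring. Visible temperature leaves those untouched.

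**A large share of admissions would be study-induced.** No such figure can be supported. A prompted contact is not an admission, and the protocol gives no rate for either. For admissions even the direction is uncertain, since an early contact might avert one.

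**Temperature is one input among many in an exploratory proof of concept.** True, and this limits the consequence to what is claimed for temperature and for models that use it.

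**Conclusion.** The inconsistency is real and can be stated with high confidence: a design property asserted for all device readings does not hold for one vital sign assigned to all participants. It rests on one inference, that a value entered by hand from a handheld thermometer has been seen by the person entering it.

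The statistical consequence is narrower. Visibility could inflate temperature's apparent predictive value for contacts initiated by a patient or carer. The size cannot be derived from the document. The count of about 156 readings per participant describes exposure, not bias. The contradiction does not extend to LifeLight, FibriCheck or the activity band, and it does not require the study's conclusion to rest on blinded signals alone; that is a modelling choice the document does not settle. The correction is chiefly one of wording, with a matching separation in the results.

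**What to change.** - Reconcile sections 1.3, 3, 3.4.1 and 4.1 by stating that readings are blinded to participants except temperature, which is read and entered by the participant or, where applicable, care-home staff.
- Limit the section 3 inference about prompted contact in the same way.
- Check that the participant information does not repeat the unqualified claim.
- Report predictive performance with and without temperature, particularly for patient- or carer-initiated contacts, and do not attribute performance gained from temperature to a blinded signal.

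Excluding contacts that participants say were prompted by a reading is not recommended. It selects on the outcome, because someone with a genuine infection may also give that answer.

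The cost is a few sentences, one extra model run and a more qualified claim for temperature.

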3.1 Participant eligibility

The research team aim to recruit 500 participants to take part in the study. In order to achieve this target number, the research team aims to identify at least 700 potential participants according to the following inclusion and exclusion criteria.

Inclusion Criteria

- Individuals over the age of 18 that:
 - Have 3 or more long-term conditions AND/OR
 - Have a medium to high frailty score AND/OR
 - Are suffering from unsteadiness or falls AND/OR
- Those who are found to have paroxysmal and/or asymptomatic atrial fibrillation (AF), hypertension or heart failure
- Live in their own homes or in residential care homes or in nursing care homes

Exclusion criteria

- Children
- Individuals for whom consent cannot be obtained (i.e. individuals with severe mental impairments or learning difficulties)
- Patients on palliative care
- Individuals lacking mental health capacity or whose mental health conditions might be influenced by participating in the study?
- Individuals who's mental capacity deteriorates during the study period will be removed from the study.

3.2 Participant selection

3.2.1 Participants living in their own homes

The research team will work with the CCG and Commissioning Support Unit (CSU) to identify suitable patients to be approached to take part in the study from pseudonymised NHS patient data.

This will involve using data analysis algorithms called the Diagnostic Stratification Technique, which has been developed by Helicon and their partner i5Health. It is based on Machine Learning, Neural Networks and Artificial Intelligence to analyse millions of clinical patterns from de-identified patient data collected by the NHS in the Hospital Episode Statistics (HES) database. HES comes from data collected by NHS Digital to provide CCGs and care providers with important information pertaining to commissioning and payment for care delivered to patients. However, it is also possible to use this data for research purposes and other secondary uses. This is because strict statistical disclosure control is applied in accordance with the NHS Digital protocol, which suppresses small numbers to stop individuals being identified from the data and ensure patient confidentiality is maintained.

The CCG will formally request Helicon and i5Health to undertake a search for their HES data to produce a list of pseudonymised patients. This list will then be passed to the CSU Data Services for Commissioning Regional Offices (DSCRO) for re-identification. This will ensure that all Information

11

Governance (IG) requirements are strictly applied. Once re-identification is complete, the CSU will be able to group patients into lists according to their registered GP practice. These lists will then be securely distributed (using NHS mail or other secure connection) to the relevant GP practices so that the participant recruitment process can begin. It is important to note that no party other than the CSU and GP practice will be able view the identifiable patient data at any point prior to formal consent being obtained from the patient directly.

Once each GP practice has a list of potential participants, GPs or healthcare professions will be able to review each patient record individually in line with the study's inclusion / exclusion criteria to make further exclusions where appropriate.

3.2.2 Participants in residential care homes & nursing homes

During preliminary engagement activities, the CCGs Clinical Lead [name] will socialise the study with residential care homes and nursing homes in the South Lincolnshire geography to gauge their appetite take part in the study and become research sites.

Those that agree to take part will be given the studies inclusion and exclusion criteria to select suitable residents who could potentially become study participants. It is very likely that residents chosen to take part by care home professionals will be included on the patient lists given to GPs above; this will be checked once formal consent has been obtained from residents.

It is anticipated that only about a third of participants will be recruited from care homes or fewer if engagement activities prove it is impractical.

3.3 Participant recruitment and consent

3.3.1 Recruitment of participants living in their own homes

The study intends to recruit 500 participants to take part in the study and will therefore aim to invite at least 700 to individuals to participate.

To do this, the research team will provide GP practices with the following participant facing documents to use in recruitment activities with their own patients:

1. Participant Invitation Letter

This will give a brief summary of the study and instructions on how to either accept or decline the invitation.

2. Participant Information Sheet (PIS)

This will provide a more detailed explanation of the study including what the participant will need to do, why we are undertaking the study, how they can withdraw from participation etc. a copy of the PIS has been submitted with this application.

3. Study Consent Form

This will be the formal consent form that participants will sign to agree to take part in the study. Due to Covid-19, consenting processes have been adapted to ensure that consent is undertaken remotely. The Clinical Research Network have confirmed that the consent form can be posted to participants as part of the initial communication. Prior to Covid-19, consent would have been obtained in a face to face meeting with a healthcare professional. Please see section 3.3.2 below for full details).

12

IRAS ID: 286225	[Proof of Concept – Smart Technology – South Lincolnshire]
CPMS: 44344	PoC Protocol Version: 1.4
01/08/2020	

4. Text Message Content

A follow up text message will be sent to those potential participants who have a mobile number recorded with their GP practice. It will refer them to the study pack sent in the post and include a link to the cloud environment where they can securely complete their consent form online.

The GP practice will send the information pack above to each potential participant and include a prepaid return envelope addressed to Optima Systems Ltd for them to return their signed consent forms. The invitation letter will also include a URL where participants can complete their consent form electronically online if they prefer. Optima Systems Ltd will collate and store signed consent forms for a period of XXXXXX

The participant will be given three options:

- 1. Sign and return the consent form if they are happy to take part (either online or by post)
- 2. Do nothing if they do not wish to take part it will be assumed that they do not want to take part if a consent form is not received within 2 weeks
- 3. Call Clinical Research Network for more information and/or to complete consent form over the phone

Potential participants are asked to complete consent forms withing one week if they would like to take part. If nothing is received after 2 weeks, they will be removed from the study invite lists by GP practices.

